the best of our knowledge, no such comparisons have yet been made in a cohort of morbidly obese (BMI \geq 40) pregnant women manifesting severe hypertension.

The conical Ultracheck Curve (reusable or single use) BP cuff (Statcorp Medical, Jacksonville, Florida, U.S.A.) is advertised (Sharn Anesthesia Inc., Tampa, Florida, U.S.A.) as: "A Breakthrough Solution for Accurate Bariatric Blood Pressure Readings. We intend to compare IBP readings obtained from morbidly obese, severely hypertensive (SBP > 160 mm Hg) parturients with NIBP consecutively measured with new innovative conical Ultracheck Curve BP cuffs and large standard upper arm rectangular cylindrical as well as radial BP cuffs.

Methods: Twenty-five morbidly obese (BMI \geq 40 kg/m²) severely hypertensive (SBP > 160 mm Hg) parturients with clinically indicated radial artery lines already in situ or who agree to placement of an arterial line after a thorough explanation of limited complications related to arterial line insertion will be recruited to the study. Both IRB approval and the patients' written informed consent for the study will be obtained. The following measurements (left and right arm) will be made and recorded with the patient lying in a 15° left lateral tilt position, arms by their side and forearms pronated:

- 1) Proximal upper arm circumference just below the axilla.
- 2) Distal upper arm circumference 0.5 cm above antecubital fossa.
- 3) Upper arm length axilla to the antecubital fossa.
- 4) Blood pressure cuff size

For comparative purposes BP will be measured and documented sequentially and in random order (computer generated random numbers table). NIBPs will be recorded using either an upper arm large adult [American Heart Association (AHA): 16-36 cm.] cylindrical BP cuff, a radial cuff, or an UltraCheck Curve bariatric BP cuff. The BP cuffs will be linked to an Oscillometric BP recording device (Philips M1574A). There will be an initial set of readings on admission, and subsequent sets of readings before a medication administration on the Vanderbilt Management Guideline for Acute Hypertension Algorithm. A set of readings will also be attained at decision for ICU transfer or cesarean section. SBP, MAP and DAP will be recorded from each cuff site (3 cuffs total) and then repeated after swapping the cuffs over to the opposite arm . Direct invasive arterial pressure readings will be charted simultaneously for comparative purposes.

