The primary outcome of this investigation will be to compare the agreement of NIBP and SBP measurements relative to IBP SBP recordings. Secondary outcomes will be: To compare the agreement of MAP and DAP NIBP recordings with IBP levels; to compare agreement of the SBP, MAP and DAP NIBP measurements obtained with cylindrical upper arm and radial BP cuffs with those recorded using conical BP cuffs.

Agreement between devices (NIBP vs IBP and NIBP cylindrical (upper and radial) versus conical BP cuffs) will be determined. The relationship between upper arm circumference minus distal arm circumference and upper arm cylindrical pressure and intra-arterial SBP difference

will be defined as well. The same relationship between upper arm minus distal arm circumference and conical cuff and intra-arterial SBP recordings differences will also be assessed.

Main Inclusion Criteria:

Written, signed and dated informed consent

 \geq 18 years of age

Morbidly obese (BMI \geq 40 kg/m²) severely hypertensive (SBP > 160 mm Hg) parturients with clinically indicated radial artery lines already in situ or who agree to placement of an arterial line after a thorough explanation of limited complications related to arterial line insertion will be recruited to the study

Gestational age greater than or equal to 24 weeks Parturients admitted for induction of labor

Exclusion Criteria:

Parturients admitted in labor

Statistical Plan:

Bland-Altman plots will be used to look at agreement of NIBP (SBP, MAP and DAP) and IBP. Regression analyses will examine the relationship between upper and lower forearm circumference measurements and difference between NIBP (SBP, MAP and DAP) cylindrical and radial cuffs versus conical (obesity) BP cuffs.

Based on the 2012 report from South Africa¹⁷ we estimate that 25 patients will initially need to be investigated. A difference of 10 mm Hg (SBP, MAP and DAP) will be considered clinically significant.

References:

- 3. Bramham K1, Parnell B, Nelson-Piercy C, Seed PT, Poston L, Chappell LC. Chronic hypertension and pregnancy outcomes: systematic review and meta-analysis BMJ. 2014 Apr 15;348:g2301. doi: 10.1136/bmj.g2301.

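### The Statistical Plan's only regression names a forearm circumference that is not measured and a cuff-versus-cuff response, so it does not deliver the cuff-minus-IBP relationships promised in the outcomes text

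*Combined protocol and SAP*

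**What the plan says.** Three places in the combined protocol and SAP bear on this.

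- **Methods, measurement list.** For each arm: "Proximal upper arm circumference just below the axilla"; "Distal upper arm circumference 0.5 cm above antecubital fossa"; "Upper arm length axilla to the antecubital fossa"; and cuff size. Readings are taken on admission, with "subsequent sets of readings before a medication administration", and again at a decision for ICU transfer or cesarean section. Each set is repeated with the cuffs moved to the other arm, and IBP is charted at the same time as each cuff reading.
- **Methods, outcomes text (just before the inclusion criteria).** A secondary outcome is "to compare agreement of the SBP, MAP and DAP NIBP measurements obtained with cylindrical upper arm and radial BP cuffs" against those from the conical cuff. Two circumference relationships are then promised: "The relationship between upper arm circumference minus distal arm circumference and upper arm cylindrical pressure and intra-arterial SBP difference", and "The same relationship between upper arm minus distal arm circumference and conical cuff and intra-arterial SBP recordings differences will also be assessed".
- **Statistical Plan.** Bland-Altman plots are planned for cuff readings against IBP, with no circumference term. The only regression is "Regression analyses will examine the relationship between upper and lower forearm circumference measurements and difference between NIBP", where the difference is that of the cylindrical and radial cuffs from the conical cuff, for systolic, mean and diastolic pressure. Nothing is said about repeated readings from the same woman.

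**The concern.** The one regression that is specified does not match the data to be collected or the relationships to be reported. Its predictor, read literally, is not on the measurement list. Its response leaves out the reference method, whereas the outcomes text wants to know how each cuff's error against IBP varies with arm shape. The analyst would have to choose predictor, response and model for the promised analysis after the data are in. Because each woman gives two arms and possibly several sets, the handling of rows is also left open, and that choice alone can decide whether a slope looks significant.

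**Working it through.** **1. Predictor.** Two circumferences are listed, proximal and distal upper arm. The distal one is taken above the antecubital fossa, so neither is on the forearm. The form differs too: the outcomes text uses the proximal-minus-distal difference (taper), while the Statistical Plan names two circumferences without a difference.

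**2. Response.** Let C and K be the cylindrical and conical readings, with A₁ and A₂ the IBP charted with each. Then

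C − K = (C − A₁) − (K − A₂) + (A₁ − A₂).

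If IBP is the same at both readings, the last term is zero. If the slopes of the two cuff-minus-IBP differences on taper are b₁ and b₂, the slope of C − K is b₁ − b₂. When b₁ = b₂ the planned regression has slope zero, however large the common slope. It can show that the cuffs differ from each other, but it cannot recover b₁ or b₂, which are what the outcomes text promises. Because the cuffs are read in sequence, any drift in IBP (A₁ − A₂) also enters C − K as noise. It does not enter the cuff-minus-IBP differences.

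**3. Promised against planned.**

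| Relationship | In outcomes text | Model in Statistical Plan |
|---|---|---|
| Taper vs cylindrical-minus-IBP SBP | yes | none |
| Taper vs conical-minus-IBP SBP | yes | none |
| Circumference vs cuff-versus-cuff difference | no (only agreement between cuffs) | yes |

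**4. Repeated rows.** The plan gives no figure to reproduce. From the documents: 25 women, two arms, one or more sets. Assumed: within-woman correlation of error ρ = 0.3 to 0.7, arm-to-arm correlation of the predictor 0.95, and no true slope. With s sets, each row shares its woman with s − 1 rows from the same arm (predictor correlation 1) and s rows from the other arm (0.95). If rows are treated as independent, the variance of the slope is understated by about

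D = 1 + ρ[(s − 1) + 0.95s],

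and the actual two-sided error of a nominal 5% test is 2[1 − Φ(1.96/√D)].

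| Sets | D at ρ = 0.3 | False positives | D at ρ = 0.7 | False positives |
|---|---|---|---|---|
| 1 | 1.285 | 8.4% | 1.665 | 12.9% |
| 2 | 1.870 | 15.2% | 3.030 | 26.0% |
| 3 | 2.455 | 21.1% | 4.395 | 35.0% |

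Simulations of 25 women agree: 8–14% with one set, 15–28% with two, 21–36% with three. If side-to-side deviations in the two circumferences are unrelated, taper correlates less between arms. With an SD ratio of 1.25 and a proximal-distal correlation of 0.8 (both assumed), Var(P − D) = 1.5625 + 1 − 2 = 0.5625, the arm-specific part is 0.05 × 2.5625 = 0.128, and the correlation is 1 − 0.128/0.5625 = 0.77. Putting 0.77 for 0.95 with three sets gives D = 2.293 to 4.017 and false positives of about 20% to 33%, so the conclusion is little changed. A mixed model with effects for woman and for set within woman, tested on woman-level degrees of freedom, held the rate at 3–6% in simulation with three sets.

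**5. What the promised regression could detect.** With 25 independent women, 80% power and two-sided 0.05 (assumed), the detectable correlation is tanh[(1.960 + 0.842)/√22] = 0.535. If the ±17 mm Hg quoted in Background and Significance for oscillometric error is an SD, that is 0.535 × 17 = 9.1 mm Hg per SD of taper. Only a strong relationship would be found, so the analysis is exploratory.

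**The case against.** The document is short and combined. A few lines above the Statistical Plan, the outcomes text already commits to the taper predictor, the cuff-minus-IBP response and the two cuffs. Forearm most plausibly stands for the two upper arm measurements, in which case the predictor data exist. The cuff-versus-cuff response also serves a stated secondary outcome. All of this stands, and it limits the point. What is missing is a model for a promised analysis and a rule for repeated rows. Correcting forearm still leaves the only specified regression with the wrong response for that purpose.

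The plan never says that rows will be treated as independent, so the false-positive rates show the cost of one reading of an omission, not of a stated method. They depend on the assumed correlations and on the number of sets.

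A reader might go further and infer that taper is the wrong predictor, because the hypothesis in Background and Significance speaks of large arm circumference. The documents do not support that. The hypothesis concerns extra under-reading in a population with large arms, which average bias against IBP addresses. It promises no gradient with size within the cohort, and taper suits a comparison of conical with cylindrical cuffs. A calculation in which taper has low power can be built by assuming that size alone drives the error, but that assumes the answer.

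**Conclusion.** The point holds as a mismatch between measurement list, outcomes text and Statistical Plan that should be reconciled before analysis. The mismatch itself rests on the text and on no assumed number. The size of the clustering problem is conditional: roughly 8–14% false positives with one set per woman and 20–36% with three, for the assumed correlations and only if rows are analysed as independent.

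Two stronger inferences should be avoided. One is that the trial would have no data on arm-related error against IBP: the upper arm circumferences, cuff readings and IBP are all to be recorded. The other is that the gap stops at the regression, leaving the primary analysis untouched. The Bland-Altman estimate of mean bias does not depend on the regression wording, but the same arms and sets feed those plots, so the limits of agreement and their confidence intervals also need the repeated readings handled.

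**What to change.** 1. In the Statistical Plan, replace the forearm wording with the measured proximal and distal upper arm circumferences. If forearm circumference was meant, add it to the Methods list.
2. Add the promised regression, separately for the cylindrical and conical cuffs: cuff-minus-IBP SBP on proximal-minus-distal circumference. Use each arm's own values, a random effect for woman (and for reading set within woman where there are several sets), woman-level degrees of freedom, and a term for whether the cuff is on the arm with the arterial line.
3. Keep the cuff-versus-cuff regression with the same random effects.
4. Use a repeated-measures form of the Bland-Altman limits of agreement and their intervals.
5. Label the regressions exploratory. Optionally add mean circumference (size) and upper arm length as further predictors.

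Cost: plan wording only, if the upper arm circumferences are meant, apart from recording which arm carries the line, which the measurement list does not mention. A forearm measurement would be a new item to collect. The optional size term has a price: if only taper matters, a joint test of both has about 71–72% power where taper alone has about 82%, a loss of about 10 points (25 independent women, true correlation 0.535).
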